4 PRIMARY ANALYSIS & SUPPORTING ANALYSES

The *primary analysis* of D2d will assess whether, in participants with pre-diabetes, oral daily vitamin D₃ supplementation reduces the rate of progression from pre-diabetes to incident diabetes (=primary outcome).

All randomized participants are included in the analysis. Kaplan-Meier estimates of “time to confirmed diabetes” distributions will be calculated for each treatment group. The log-rank test will then be used to perform an unadjusted comparison of the time-to-event distributions in the two treatment groups. Follow-up of participants who do not complete the study (e.g. withdrew) will be "censored" on the date of their last follow-up encounter (see below). Cox proportional hazard modeling will be used to compare the risk of incident diabetes in the two groups.¹ The model will include an indicator for the randomized intervention as its main predictor variable. Clinical site at randomization will be a stratifying factor. The baseline variables (BMI, race, as entered in SPIRS) used to stratify the randomization will also be included as stratifying factors.

The p-value from the primary analysis will be based on the chi-square statistic from a likelihood ratio test obtained from proportional hazards models with and without the term for intervention arm. Comparisons of the intervention groups will be performed per the ITT principle, with all randomized participants grouped per their intervention assignment at randomization, regardless of adherence. Unless otherwise specified, p values will be two tailed, and values below 0.05 are considered statistically significant.

Definitions of follow-up time and censoring. Follow-up time for the primary outcome will be censored at the date of the *last assessment for diabetes with data in the electronic data capture system as of the cutoff date (as defined in the Manual of Procedures – section 20)*.

Censoring for participants *with diabetes* occurs at the date of the diabetes event, as shown in the *Diabetes Outcome* form in EDC. Specifically,

- If the diagnosis of diabetes is made within the study (i.e., using results by the Central Laboratory), the date of onset of diabetes is defined as the date of the first diagnostic glycemc value.
- If the diagnosis of diabetes is made outside of study (i.e., adjudicated), the date of onset of diabetes is determined during the adjudication process.

Censoring for participants *free of diabetes* occurs at one of the following dates:

- Death or active withdrawal.
- Last encounter *free of diabetes*, using the most recent of the following 3 options:
 - Scheduled encounter
 - Semi-annual visit (*or non-visit contact*)
 - Annual visit (*or non-visit contact*)
 - Interim phone call
 - Unscheduled visit to evaluate for diabetes in between semi-annual/annual visits [as described in Manual of Procedures – section 18].
 - Adjudicated event (that did not confirm diabetes).

Sensitivity analysis of the primary analysis

Competing event of diabetes medication use

The use of a diabetes medication (e.g., metformin for worsening pre-diabetes or for new diabetes diagnosed outside of D2d) is considered a “competing event.” Specifically, if vitamin D supplementation is presumed to be effective at reducing diabetes risk, more participants in the placebo group will be placed on a diabetes medication (e.g., metformin) for worsening pre-diabetes or early stage diabetes. If these participants do not meet the D2d criteria (i.e., by central laboratory criteria or adjudication) when starting a diabetes medication, they continue to be followed for incident diabetes within D2d, per ITT analyses. However, *the use of a diabetes medication in these participants practically removes them from the potential pool of those likely to meet the incident diabetes endpoint as the diabetes medication will improve glycemia. Such competing events reduce the power of the trial by lowering diabetes risk.* Importantly, because starting on a diabetes medication is more likely to occur in the placebo group – if the underlying hypothesis holds – these events falsely change the relative risk reduction towards null. Cases in which a diabetes medication has been started without the participant meeting the D2d criteria for diabetes are not uncommon because of local clinical practice or laboratory variability between the central D2d laboratory and local laboratories.

To examine the potential effect of these “competing events” on study fidelity, *in sensitivity analyses*, the primary endpoint will be defined as “*time to incidence diabetes by D2d criteria or use of a diabetes-specific medication.*” This analysis includes participants that started and remained for more than 31 days on a diabetes-specific medication (for worsening glycemia, for weight loss or for any other reason) but the D2d criterion of incident diabetes was not made (by central laboratory criteria or adjudication). In this analysis, follow-up of participants for the primary outcome is censored at the time when the diabetes-specific medication begun.

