At the baseline visit, a 75-gram OGTT will be performed to obtain blood for FPG, 2hPG and HbA1c to confirm the glycemic eligibility criteria, urine will be collected to assess the calcium-creatinine ratio eligibility criterion and physical examination will be done. The Central Laboratory will conduct the analyses of tests obtained at the baseline visit. Volunteers who meet the eligibility criteria at the screening visit *and* the physical examination, and glycemic and urine criteria at the baseline visit (measured by the Central Laboratory) will be invited to the randomization visit.

Multiple screenings are allowed for participants who missed the inclusion/exclusion criteria by a small margin. For example, if a participant does not qualify due to high blood pressure, she may return for screening after her hypertension is treated. It will be up to the site PI to decide when a participant may return for re-screening.

If a potential participant has recent glycemic results (FPG and HbA1c) that meet the screening criteria, he may proceed directly to a combined screening/baseline visit, as long as the visit occurs within 6 months of these tests. During this combined visit, all screening procedures will take place, including blood tests that have not been done by the local laboratory within the last 6 weeks. At this combined visit, blood and urine will be collected for baseline measurements and processed but sent to the central laboratory *only if the participant meets all other screening criteria*.

Figure 6.1: Flow diagram of assessment of eligibility at screening and baseline visits

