9.1 Primary Endpoint (Outcome)

The primary outcome will be *time to progression from pre-diabetes to incident (new-onset) diabetes, defined by laboratory criteria*, as follows:

Laboratory diagnosis of diabetes, based on the following ADA glyceic criteria²⁶² measured at study visits: FPG \geq 126 mg/dL, 2hPG \geq 200 mg/dL **and/or** HbA1c \geq 6.5% (Figure 9.1.1 and 9.1.2).

All three glyceic measures will be assessed at scheduled yearly visits by conducting a 75-gram OGTT (Figure 9.1.1). If all three glyceic measures are negative for diabetes, then the participant does not have diabetes and will continue on the assigned treatment. If two or all three of the glyceic measures are positive for diabetes, the participant will be considered to have reached the diabetes outcome and no confirmatory testing is required. If only FPG or HbA1c is positive for diabetes, then a confirmatory visit to repeat the *same glyceic test that was positive* will be completed within 8 weeks. If the repeat measure is also positive for diabetes, then the participant will be considered to have reached the diabetes outcome. For example, HbA1c = 6.5% and FPG = 119 mg/dL at the scheduled annual follow-up visit and HbA1c = 6.6% at the confirmatory visit. If only the 2hPG is positive for diabetes, then a confirmatory visit (with an OGTT) to repeat all three glyceic measures will be completed within 8 weeks. If the repeat 2hPG is positive for diabetes, then the participant will be considered to have reached the diabetes outcome. If the repeat 2hPG is negative for diabetes but *both* repeat HbA1c and FPG are positive for diabetes, then the participant will be considered to have reached the diabetes outcome. Otherwise, the participant does not have diabetes and will continue on the assigned treatment.

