The table immediately below displays the expected numbers of incident diabetes cases in the placebo group at each semi-annual visit based on transition probabilities derived from the assumed incidence rates of progression and loss-to-follow-up, and the assumption of constant hazard rates for events and loss-to-follow-up. This calculation also assumes that, when study closeout begins, all participants will return for an end-of-study visit, which will include testing for incident diabetes. The table also displays the expected number of events in the vitamin D supplementation arm if treatment reduces the hazard rate by 25%. Given the assumed uniform rate of recruitment over a period of 2 years, the number of events expected to occur within 2 years after the date of last enrollment or at the close-out visit is 586 (293*2) under the null hypothesis and 521 (293 + 228) under the alternative hypothesis. Thus, the study will be very likely to reach the required number of events within four years if vitamin D supplementation is not effective and all other assumptions are satisfied, and will reach that target of events within the same time period with probability greater than 0.50 if treatment reduces diabetes incidence by 25%.

Table 1. Expected number of events at each six-month visit in the placebo and vitamin D arm (under the alternative hypothesis).

	Visit								Total
	M06	M12	M18	M24	M30	M36	M42	End-of-study	
Placebo	60.4	55.9	51.7	47.8	33.1	20.4	9.4	14.3	293
Treatment	45.6	42.7	40.0	37.5	26.3	16.5	7.7	11.6	228

Number of events is approximate. End-of-study visit will coincide with a scheduled visit (semi-annual or annual).

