We expect the diabetes incidence rate in the D2d study to be at the high end of the rate that would be predicted from the mean annual incidence rate (~9-11%) reported in previous diabetes prevention studies because: (1) the study is targeting a population similar to the DPP (U.S. adults at high risk for type 2 diabetes with similar BMI and age at entry); (2) the definition of ‘at risk for diabetes’ requires 2-out-of-3 glycemic criteria, which will identify participants at higher risk for progression to diabetes; (3) the study will use the current ADA glycemia criteria for diagnosis of diabetes (addition of HbA1c), which will likely raise the incidence rate of diabetes compared with the above studies.

In relation to point (3) above, only one of the published studies on prevention of type 2 diabetes included HbA1c as a criterion for both inclusion and outcome assessment.¹³ The study reported a conversion rate to diabetes in the placebo arm of 36% over 2.8 years. However, this study was conducted in Japan and its definitions of pre-diabetes or diabetes were not consistent with the current ADA criteria; therefore, its relevance to the D2d study is not clear. Adding HbA1c alters the epidemiology of pre-diabetes and diabetes and makes it difficult to predict incidence rates. We reviewed relevant data from recent cross-sectional observational studies that have evaluated the impact of adding HbA1c as a diagnostic criterion. As expected, there is considerable overlap between the HbA1c and FPG/2hPG criteria. Overall, the addition of HbA1c appears to increase prevalence of both pre-diabetes and diabetes.²⁷⁰⁻²⁷⁵ For example, Lu et al identified 37% more individuals as having

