Kaplan-Meier estimates of “time to confirmed diabetes” distributions will be calculated for each treatment group. The log-rank test will then be used to perform an unadjusted comparison of the time-to-event distributions in the two treatment groups. Follow-up of participants who withdraw or are lost to follow up will be “censored” on the date of their last follow-up visit. All p values examined for statistical significance will be two tailed, and p-values below 0.05 will be considered statistically significant. Cox proportional hazard models²⁷⁸ will be used to calculate an estimate of the adjusted hazard ratio. To construct the model for the adjusted analysis, we will first construct a regression model that does not include the indicator for treatment group. Age, race, ethnicity, BMI, and other variables (fasting glucose, 2-hr glucose, HbA1c and 25OHD) to be specified a priori will be forced into the model. Variables will then be added in a step-up fashion from a list of candidates selected a priori. Covariates making a statistically significant contribution to the proportional hazards regression model will be included in the multivariate model. When the step-up procedure has been completed, the covariate for treatment group will be added to the model. The regression coefficient for treatment group in this multiple regression model will be the adjusted estimate of the log hazard ratio.

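### The SAP's primary Cox test is valid but leaves out baseline FPG, HbA1c and 2hPG, and the SAP keeps no glycaemia-adjusted hazard ratio

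*SAP*

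**What the plan says.** SAP section 4 fits a Cox model in which "The model will include an indicator for the randomized intervention as its main predictor variable". Clinical site and the BMI and race factors from randomisation enter as strata. "The p-value from the primary analysis will be based on the chi-square statistic from a likelihood ratio test", comparing the models with and without the arm term. No further covariate is named.

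Protocol 11.2 compares the arms with an unadjusted log-rank test and separately promises an adjusted HR. For that model age, race, ethnicity, BMI and "other variables (fasting glucose, 2-hr glucose, HbA1c and 25OHD) to be specified a priori will be forced into the model". Step-up selection from a candidate list follows, and then: "The regression coefficient for treatment group in this multiple regression model will be the adjusted estimate of the log hazard ratio".

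The remaining SAP analyses of the primary outcome do not replace that estimate. Section 4 has one sensitivity analysis, which redefines the endpoint for use of diabetes medication. Section 4.3.1 uses baseline glycaemia only as subgroup categories with interaction tests. Section 7 announces unspecified checks of the censoring assumption. SAP section 1 says that some protocol analyses were removed as being of doubtful value, but does not list them.

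**The concern.** The omitted variables are the natural covariates here. They are the components of the endpoint (Protocol 9.1: "All three glyceic measures will be assessed at scheduled yearly visits by conducting a 75-gram OGTT"). They are available before treatment from one laboratory (Protocol 6.5: "The Central Laboratory will conduct the analyses of tests obtained at the baseline visit"). The protocol treats glycaemic status as prognostic (section 11.1.1: the risk definition "requires 2-out-of-3 glycemic criteria, which will identify participants at higher risk for progression to diabetes").

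In an event-driven trial the number of events is fixed. Adjusting for strong baseline predictors then gives equal or higher power at the same type I error. Two things are at stake: that gain, and an estimate which the protocol promised. An adjusted HR produced after unmasking without pre-specification would be open to the charge of post-hoc choice.

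**Working it through.** **The plan's own figure.** Protocol 11.1 gives two-sided alpha 0.05, power 90% and HR 0.75, with 1:1 allocation. By Schoenfeld's formula:

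D = 4(z₀.₉₇₅ + z₀.₉₀)² / (ln 0.75)² = 4 × (1.960 + 1.2816)² / (0.2877)² = 4 × 10.507 / 0.08276 = 507.8, rounded up to 508.

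The stated 508 is reproduced. The same formula needs 527 events for 91% power and 548 for 92%.

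**Which HR is 0.75?** Protocol 11.1 does not say whether it is the ratio between arms as a whole or the ratio at a given baseline glycaemia. Its Table 1 gives the "expected number of events in the vitamin D supplementation arm if treatment reduces the hazard rate by 25" per cent, computed from a single hazard per arm. That points to the arm-level reading. Both readings are shown below.

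**Simulation inputs from Protocol 11.1.** N = 2,382; uniform 2-year accrual; placebo hazard 0.1054; loss hazard 0.0513; data cut at event 508.

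**Assumed inputs.**
- 20 sites × 2 BMI × 2 race groups = 80 strata. At 100 to 150 participants per site (Protocol 6.2), 2,382 participants imply about 16 to 24 sites.
- Permuted blocks of 4.
- Three glycaemic covariates with pairwise correlation 0.3.
- S, the SD of the log-hazard that they jointly explain. The HR per SD of the combined score is exp(S): 1.35, 1.65 and 2.01 for S = 0.3, 0.5 and 0.7.

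**Test.** Stratified Cox likelihood ratio test of the arm term, rejecting above 3.84, fitted (a) with treatment only and (b) with treatment plus the three covariates. For the arm-level reading, the conditional HR was set to 0.746, 0.742 and 0.734 so that the treatment-only HR averages 0.75.

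| S | Arm-level 0.75: (a) | (b) | Conditional 0.75: (a) | (b) |
|---|---|---|---|---|
| 0.3 | 89.6% | 90.1% | 88.5% | 88.8% |
| 0.5 | 89.8% | 91.2% | 86.7% | 88.3% |
| 0.7 | 89.2% | 91.6% | 86.2% | 89.2% |

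There were 4,500 replicates for arm-level S = 0.5 and 0.7, and 2,500 for the others. The Monte Carlo SE of a paired difference is 0.3 to 0.5 points. The SE of a single power figure is about √(0.9 × 0.1 / 2,500) = 0.6 points, so arm-level column (a) is consistent with 90%.

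**Repeat runs, arm-level reading.**
- 80 strata, 1,200 replicates: 89.6% vs 90.8% at S = 0.5; 90.6% vs 93.6% at S = 0.7. One further run at S = 0.7 gave a gain of 3.6 points.
- 80 strata, single glycaemic score, Wald test: 89.6% vs 93.1% at S = 0.8.
- Unstratified, single score, Wald test: 90.0% vs 90.3% at S = 0.3; 90.9% vs 91.4% at 0.5; 89.6% vs 93.8% at 0.8; 88.8% vs 95.9% at 1.0. By mean Z, the saving in events is about 2%, 6%, 16% and 24%.

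**Other covariate structures (S = 0.5, arm-level).** The gain was 0.7 points when the covariate effect fades over follow-up, 1.8 for a step effect at the top quartile, and 2.1 when only one of the three values is prognostic.

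**Validity.** Under the null, rejection was 4.7 to 5.5% for (a) and 4.6 to 5.5% for (b), including the misspecified forms.

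**Estimates.** Under the arm-level reading the mean HR was 0.749 for (a) vs 0.742 for (b) at S = 0.5, and 0.749 vs 0.734 at S = 0.7. The difference is non-collapsibility of the HR, not bias in either model.

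**The case against.** The case for leaving the plan alone is substantial. The SAP test is valid and already conditions on site, BMI and race. The protocol's own comparison in section 11.2 was an unadjusted log-rank test (although its synopsis calls it adjusted), so the SAP takes away no promised power. The protocol's adjusted model relied on step-up selection, which is a fair reason to drop it. All of this stands, but the glycaemic covariates were to be forced in and needed no selection, so it does not explain their removal.

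The size of the gain is assumed. Eligibility confines at least two of the three values to narrow ranges and caps all of them below the diabetes thresholds, which limits their spread. The estimated gain at S = 0.5 varies from 0.5 to 1.4 points between runs, and differences of that order are close to simulation noise. Overrun at close-out could matter as much: at the 521 events that Protocol 11.1 expects under the alternative, Schoenfeld power is about 90.7%. These points limit how much weight the power argument can bear.

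Protocol 11.2 also plans a formal interim look at 70% of events, and the documents do not say whether it came before this SAP version. If it did, changing the primary statistic is a larger step than adding a sentence. The supporting-analysis route avoids that difficulty.

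Finally, a three-covariate model is a fixed replacement for the protocol's adjusted HR, not a copy: age, ethnicity and 25OHD are not in it. The case for omitting 25OHD is thin. The sub-cohort note in SAP 5.2 concerns change-from-baseline analyses, and SAP 4.3.1 uses baseline 25OHD for the primary outcome without such a limit. The main reason for stopping at three is that these are the endpoint's components.

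**Conclusion.** The concern holds, as an improvement forgone and not as an error. The SAP's primary model contains no baseline FPG, HbA1c or 2hPG, and no other SAP analysis gives a glycaemia-adjusted HR for the primary outcome.

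If 0.75 is the arm-level HR, power is about 90% as planned. Adjustment would add roughly 0.3 to 0.5 points at S = 0.3, 0.5 to 1.4 at S = 0.5 and 2.4 to 3.6 at S = 0.7, and more if glycaemia is more strongly prognostic. If 0.75 is conditional on glycaemia, the present test has 88.5% to 86.2% power over S = 0.3 to 0.7, and adjustment recovers 0.3 to 3.0 points.

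These sizes rest on the assumed S, for which the documents give no value. The loss of the promised adjusted estimate does not depend on S. It is worth changing, with medium confidence in the size of the benefit.

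**What to change.** Before unmasking, amend SAP section 4 in one of two ways.

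1. **Preferred:** add continuous central-laboratory baseline FPG, HbA1c and 2hPG as fixed covariates to both models of the primary likelihood ratio test. Keep the site, BMI and race strata, use no step-up selection, and report the present treatment-only stratified model as supportive.
2. **If the primary test is to stay as it is:** name the same fixed-covariate model as a supporting analysis, so that a pre-specified glycaemia-adjusted HR is still reported.

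Either way, say that this model replaces the adjusted HR of Protocol 11.2, and how a missing baseline value is handled so that every randomised participant stays in the analysis.

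The cost is one or two sentences, and the data already exist. There are two drawbacks. The adjusted HR is conditional on baseline glycaemia and should be labelled so. The model also assumes log-linear, proportional covariate effects; in the checks above, a wrong form at worst cut the gain to 0.7 points and left type I error near 5%.

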7.6 Adherence with Study Procedures and Study Pills

Participants' adherence to study procedures is critical to the successful conduct of D2d, especially because of its impact on power; therefore, the study will aim to maximize adherence, by taking the following steps: (1) Prevent/minimize potential adherence problems before participant enrollment, as follows: the study design has kept the intervention (i.e. single daily dose study pill regimen) and follow-up procedures uncomplicated; the informed consent process will emphasize the importance of adherence; exclusion criteria include those with higher probability of non-adherence. (2) Maintain/enhance adherence during the trial, as follows: participants will be seen three times during the first 6 months (at baseline, 3-month and 6-months) and every 6 months for the remainder of the study; at the midpoint of each 6-month interval, participants will receive a telephone call to encourage adherence, assess for adverse events or changes to medical history and concomitant medication use and be reminded to report the diagnosis of diabetes outside of D2d or planned (or actual) use of any new medications (especially diabetes medications) and be reminded of their upcoming visit (alternatively, participants may also be contacted via email, or text based on their preference); study staff will provide participants with a personalized study calendar with visit dates; at every visit, participants will also receive information and tips to promote retention and adherence to study procedures; each site PI, co-investigators, research coordinator and staff will be available to answer participants' questions and will maintain a flexible schedule to meet the participants' needs; sites will also employ a variety of site-specific methods to promote retention by maximizing rapport with participants and their families (e.g. holiday and/or birthday cards). (3) Monitor adherence during the study based on pill counts (at every 6-month visit). Individual adherence to study medication will be defined as a pill intake over 80% based on pill counts. If a participant does not meet the adherence minimum target of 80% at any visit, s/he will be reminded of the importance of adherence to the study's objectives, the administration instructions will be reinforced and the site research staff will work with the participant to identify causes that contribute to suboptimal adherence and develop approaches to overcome barriers to adherence. Adherence during the study will also be monitored by measurement of the physiological response biomarker to vitamin D supplementation (plasma 25OHD concentration) at yearly intervals. A pre-specified absolute level of increase in 25OHD concentration cannot be used for adherence for each participant given the individual variation in response to supplementation, although it is expected that adherent participants will have a rise in 25OHD concentration from baseline. *The 25OHD concentration will not be available in real-time as measurements will be conducted at the end of the study.* Planned analyses will test for effect modification by adherence based on (1) adherence based on pills counts and (2) achieved plasma 25OHD concentration (see Section 11).

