2 STUDY POPULATION & TREATMENT GROUPS

Defining the Study Population and Treatment Groups - The primary analysis is intention-to-treat (ITT), including all randomized participants in their assigned treatment arm and including *all diabetes events observed during the study*, irrespective of adherence to assigned treatment. For all participants, follow-up will be censored at the date of the last assessment for incident diabetes (see section 4).

Every effort has been made to establish eligibility prior to randomization; however, 13 participants (0.05% of the cohort) have been subsequently found not to meet all eligibility criteria. Some of these participants were ineligible because of a safety exclusion criterion and are not on study pills. Consistent with the ITT principle, participants who did not meet eligibility criteria will be included in all analyses. This proportion (0.05%) is considered small and, consistent with the data analysis plan in the protocol, does not warrant sensitivity analyses to assess the impact of excluding those individuals from the analyses.

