3 OUTCOME VARIABLES

3.1 Primary outcome

The primary endpoint is time to incident diabetes, as described in the protocol and Manual of Procedures 18.

Cases of diabetes diagnosed outside of D2d (i.e., during routine clinical practice) among “inactive” participants that are discovered incidentally by D2d research staff will not count as diabetes cases and will not be included in the primary analysis.

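### Does the SAP's list of censoring encounters, which includes phone calls, undermine its rule to censor at the last diabetes assessment?

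*SAP*

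**What the plan says.** SAP section 2 states that for everyone "follow-up will be censored at the date of the last assessment for incident diabetes". The paragraph on follow-up time and censoring in SAP section 4 uses nearly the same words: "last assessment for diabetes with data in the electronic data capture system as of the cutoff date".

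Earlier in section 4, participants who do not complete the study are censored "on the date of their last follow-up encounter (see below". The list that follows gives, for participants free of diabetes, either death or active withdrawal, or "Last encounter *free of diabetes*, using the most recent of the following 3 options". Those options are a scheduled encounter, an unscheduled visit to evaluate for diabetes, and an adjudication that did not confirm diabetes. Scheduled encounters include the "annual visit (*or non-visit contact" and the "Interim phone call".

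SAP section 3.1 adds that outside diagnoses among inactive participants "that are discovered incidentally by D2d research staff will not count as diabetes cases".

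Protocol section 11.2 censors withdrawn or lost participants at their last visit. Protocol section 7.6 says that at the mid-interval calls participants will "be reminded to report the diagnosis of diabetes outside of D2d or planned (or actual) use of any new medications". Section 8.1 asks staff at every contact to tell participants to report an outside diagnosis promptly. Section 9.1 sends such reports to study testing or adjudication.

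**The concern.** The primary endpoint rests on laboratory criteria, and the Schedule of Procedures shows no FPG, HbA1c or OGTT at phone contacts. A person reached only by phone can cross the diagnostic threshold unseen and still be counted as at risk and diabetes-free. If such time is credited, incidence is understated. Two details add to the worry. The list accepts a non-visit contact in place of an annual visit, whereas Protocol section 7.4 describes phone substitution only for semi-annual visits. And SAP 3.1 discards some outside diagnoses in inactive participants without saying whether contact with them extends follow-up.

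At stake would be an ambiguous primary time variable, Kaplan-Meier curves that are too low and, if untested contact differed by arm, a biased hazard ratio.

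**Working it through.** **1. The plan's own figure.** Inputs from Protocol 11.1: HR 0.75, two-sided alpha 0.05, power 90%, 1:1 allocation. Schoenfeld: 4 × (1.960 + 1.282)² / (ln 0.75)² = 507.8, so 508 events, as stated. Power at 508: Φ(0.2877 × √508 / 2 − 1.96) = 0.900. Censoring dates do not enter this calculation.

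**2. Why the hazard ratio is insensitive.** Both rules count the same events, namely laboratory diagnoses plus adjudicated outside diagnoses. They differ only in how long event-free people stay in the risk set. Each event contributes n₁·HR / (n₁·HR + n₀) to the Cox likelihood, where n₁ and n₀ are the numbers at risk in the two arms. If both are inflated by the same factor, the term is unchanged.

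This was simulated with the protocol's inputs: N 2,382, event hazard 0.1054, loss hazard 0.0513, 2-year accrual, tests every 6 months. The simulation gives about 589 events under the null and 523 under HR 0.75 (protocol: 586 and 521). Every lost participant was then kept in untested contact for an assumed gap after the last test, with no diagnoses captured and equal loss in the arms:

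| Gap (years) | Extra person-time | Placebo rate per 100 person-years, last test → last contact (HR 1 runs) |
|---|---|---|
| 0.25 | +1.3% | 10.26 → 10.12 |
| 0.5 | +2.6% | 10.31 → 10.05 |
| 1 | +4.8% | 10.24 → 9.77 |
| 2 | +8.1% | 10.27 → 9.50 |

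The hazard ratio moved by about 0.001 at most.

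**3. Size of the Kaplan-Meier shift.** True 3-year placebo incidence is 1 − exp(−0.1054 × 3) = 27.1%. Planned attrition by 3 years is 1 − exp(−0.0513 × 3) = 14.3%, within the 15% maximum in the Synopsis. Let a share s of those who stop testing stay in phone-only contact.

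If none of their diagnoses is captured, the list has a closed form. Per half-year, onset has hazard 0.0527 and probability q = 1 − exp(−0.0527) = 0.0513. The hazard of moving to phone-only contact is c = s × 0.0513 × 0.5. Then

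F = q·e^(−c) × [1 − e^(−6(0.0527 + c))] / [1 − e^(−(0.0527 + c))].

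- s = 0: 27.1%
- s = 0.25: 26.5%
- s = 0.50: 26.0%
- s = 1 (upper bound): 24.9%

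Last-test censoring gives 27.1% throughout, because nothing is recorded after the last test.

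**4. With capture of outside diagnoses.** Simulated, with diagnosis 0-6 months after onset:

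| Phone-only share | Capture | List | Last test |
|---|---|---|---|
| 25% | 50% | 26.8% | 27.3% |
| 25% | 75% | 26.9% | 27.4% |
| 50% | 50% | 26.5% | 27.5% |
| 50% | 75% | 26.7% | 27.7% |

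The list is low by 0.2-0.6 points and the last-test rule is high by 0.2-0.6 points. An independent rerun agreed to about 0.1 point. At 60% capture with half phone-only, the two errors are equal (0.5 points each way). Above that, the list is closer.

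**5. The substitution the protocol describes.** Under Protocol 7.4 a missed semi-annual visit is held by phone and the participant returns at the next annual visit. With 10-30% of semi-annual visits from M18 held this way, the list gives 27.1%, which is unbiased, and last-test censoring gives 27.2-27.4%.

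**6. Against sampling error.** With 2,382 / 2 = 1,191 per arm, even without censoring the standard error is √(0.271 × 0.729 / 1,191) = 1.3 points. A 0.6-point shift is under half of that.

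**The case for a change.** The strongest opposing case is that a primary time variable should have one definition before unmasking, and that a call without a blood test is not an assessment. The SAP itself lists an unscheduled visit to evaluate for diabetes separately from a phone call, which suggests that it sees the difference. Censoring at the last glycaemic test would match the words it uses twice and would cost little.

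The mismatch in wording stands. The case for last-test censoring is weaker.

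- That rule counts outside diagnoses made after the last test but drops event-free time after it, so follow-up depends partly on outcome and incidence is biased upwards.
- It leaves participants with no post-baseline test undefined. At the planned loss hazard, 1 − exp(−0.0513 × 0.5) = 2.5% stop before M06, about 60 of 2,382. Their last test precedes randomization.
- The protocol does not support it either. It censors at the last visit, and the M03 visit has no glycaemic test. Death and active withdrawal, also on the SAP list, are not test dates.

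A hazard ratio bias would need an arm imbalance. With twofold different loss (hazards 0.0513 and 0.0253), two years of untested contact for every lost participant and no capture, a true HR of 1 reads 1.04 or 0.96. A planned HR of 0.75 reads about 0.79 or 0.73, and the rejection rate moves from about 91% to 81% or 97%. That is an extreme case in a masked placebo trial, and the documents give no sign of it.

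The inactive-participant gap is narrow. Protocol 8.6 uses that status for people lost to follow-up, who by that definition have few contacts to credit.

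**Conclusion.** No change to the plan follows. The general statements say assessment and the list says encounter, but the list is the specific instruction, section 4 sends the analyst to it, and it can be programmed as written. Time during which a reported diagnosis can become an event is reasonably counted as time at risk. Participants who complete the study end at a scheduled visit with glycaemic testing (Protocol 8.1), so the choice matters mainly for people who stop attending.

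The effect is a Kaplan-Meier shift of 0.2-0.6 points in either direction at 25-50% phone-only and 50-75% capture, and at most 2.2 points low (24.9% against 27.1%) if all attrition is phone-only and nothing is captured. The hazard ratio, the likelihood-ratio test and power are unaffected when the arms are alike. The phone-only share and the capture rate are assumptions, and no document gives either, so neither rule can be called less biased. Choosing between them is a fair trade-off. Protocol 11.2 and SAP section 7 already promise sensitivity analyses for informative censoring. The Manual of Procedures sections that the SAP cites (18 and 20) were not available and may settle the remaining wording.
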